9.3.4 SAFETY ANALYSES

The number of adverse events will be tabulated by grade and symptom/lab parameters. Proportions and corresponding 95% exact confidence intervals will be provided.

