2.2 POTENTIAL RISKS AND BENEFITS

2.2.1 KNOWN POTENTIAL RISKS

According to the FDA- approved package insert, telmisartan is contraindicated in individuals with a history of known hypersensitivity to the drug or its components and in individuals with diabetes who are also receiving concomitant aliskiren. It is not recommended in pregnant or breast feeding female because it can reduce fetal renal function and increase fetal and neonatal morbidity and death. NSAIDs is believed to increase risk of renal impairment and loss of anti-hypertensive effect. Co-administration with digoxin increases the digoxin peak plasma concentration (49%) and in trough concentrations (20%). Reversible increases in serum lithium concentrations and toxicity have been reported during concomitant administration of lithium.

The drug has been evaluated for safety in more than 3700 subjects in clinical trials, including 1900 for over 6 months and more than 1300 for over one year. Adverse experiences have generally been mild and transient in nature and have infrequently required discontinuation of therapy. In placebo-controlled trials, the overall incidence of adverse events was similar to that in patients treated with placebo. Adverse events occurring at an incidence of $\geq 1\%$ in patients treated with telmisartan and at a greater rate than in patients treated with placebo, irrespective of their causal association, were as below:

	Telmisartan n=1455 %	Placebo n=380 %
Upper respiratory tract infection	7	6
Back pain	3	1
Sinusitis	3	2
Diarrhea	3	2
Pharyngitis	1	0

The incidence of adverse events was not dose-related and did not correlate with gender, age, or race of patients. Warning and precautionary measures recommended in the package insert include the need to correct or follow closely patients who are volume- or salt-depleted; and to monitor for risk of hyperkalemia particularly in those with advanced renal impairment, heart failure or on renal replacement therapy.

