6.4 LABORATORY PROCEDURES/EVALUATIONS

6.4.1 CLINICAL LABORATORY EVALUATIONS

Hematology: Complete blood count (CBC)

Chemistries: Chemistry to include sodium (Na), potassium (K), chloride (Cl), bicarbonate (HCO₃), creatinine, blood urea nitrogen (BUN), aspartate aminotransferase (AST), aminotransferase (AST), alkaline phosphatase (ALK-P), total bilirubin, albumin, and glucose. In addition, LDH and hs-CRP will be assessed serially.

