7.4.4 EVENTS OF SPECIAL INTEREST

Not applicable.

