7.6 SAFETY OVERSIGHT

7.6.1 ROUTINE SAFETY OVERSIGHT

Safety oversight will be under the direction of the PI from first participant screening through study completion. Safety labs are done at entry (to establish baseline) and at each subsequent study visit at day 4, 10 and 21. The results of these safety labs are reviewed by the research nurse within 24 hrs of the blood draw and any concerning abnormality reviewed with the research physician. The status of all participants on study are reviewed at weekly staff meetings.

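### Section 9 specifies no between-arm analysis of potassium or creatinine as continuous values, although each is measured at baseline and at three on-treatment visits

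*Combined protocol and SAP*

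**What the plan says.** Section 2.2.1 passes on the package-insert advice "to monitor for risk of hyperkalemia particularly in those with advanced renal impairment, heart failure or on renal replacement therapy". It also states that "NSAIDs is believed to increase risk of renal impairment".

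Section 6.4.1 puts both analytes in the safety panel: "Chemistry to include sodium (Na), potassium (K), chloride (Cl" and, in the same list, "creatinine, blood urea nitrogen (BUN". On timing, 7.6.1 says "Safety labs are done at entry (to establish baseline) and at each subsequent study visit at day 4, 10 and 21". Each participant should therefore have one baseline and three on-treatment values of each.

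The specified safety analyses are these:

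- 9.3.4: "The number of adverse events will be tabulated by grade and symptom/lab parameters", with proportions and exact 95% intervals.
- 9.3.3: AE frequencies by arm, compared by chi-squared or Fisher's exact test.

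The t-test, Wilcoxon and mixed-model plan in 9.3.3 is written for secondary efficacy endpoints: RAS components, inflammatory and coagulation biomarkers, and cell counts. The analyte table in 6.4.2 lists neither potassium nor creatinine.

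Three general provisions touch on the subject. Section 9.3.1 promises 95% intervals for efficacy and safety estimates, giving averages and proportions as examples. Section 9.3.6 plans graphs of longitudinal profiles by arm. Section 9.3.10 lists individual data by measure and visit. None names a laboratory safety variable or sets an arm contrast.

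**The concern.** Safety and tolerability is the first secondary objective. Potassium and creatinine are the routine laboratory values closest to the risks that 2.2.1 names. The plan models the trajectories of a long list of exploratory biomarkers, but the specified analysis of these two values works through AE grades.

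With 20 per arm, few participants may cross a grade cut. A drug-related shift in the mean could then sit in the database while the AE table shows little or no difference. Section 12.4.1 expects a favourable result to support grant applications for further work. An unremarkable graded table could be carried forward as reassurance that it is too coarse to give. An estimated arm difference with its interval would show what the trial can and cannot exclude.

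**Working it through.** **Inputs from the documents.** 20 per arm, 5% type-I error, detectable standardised difference 0.9 (9.3.1, 9.4). The sidedness of the t-test and AE tests is not stated; two-sided is used below.

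**Assumptions.** The grade cut-points are in an external table and neither analyte has an SD in the documents. I therefore take normal values with a common SD and let the share of placebo participants above the cut, p_C, vary. The 0.9 SD shift is borrowed from 9.4, where it describes a generic Gaussian outcome; it is not a forecast for potassium or creatinine. No dropout is applied.

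**Step 1: the plan's own figure.** Section 9.4 claims above 80% power at d = 0.9.

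- Noncentrality = d × √(n/2) = 0.9 × √10 = 2.846.
- Normal approximation: Φ(2.846 − 1.960) = Φ(0.886) = 81.2%.
- Exact noncentral t, 38 df, two-sided: 79.2%. One-sided: 87.5%.

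The two-sided result is within a point or so of the stated 80%, so the figure reproduces.

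**Step 2: the same shift after grading, single visit.** The telmisartan exceedance is p_T = 1 − Φ(z − 0.9), where z is the cut in SDs above the placebo mean. Power is the sum of Binomial(20, p_T) × Binomial(20, p_C) probabilities over all tables with p ≤ 0.05.

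| Cut z (SD) | p_C | p_T | Fisher | Chi-squared, uncorrected | Means (t-test) |
|---|---|---|---|---|---|
| 2.00 | 2.3% | 13.6% | 8.2% | 19.2% | 79.2% |
| 1.64 | 5% | 22.8% | 23.9% | 37.7% | 79.2% |
| 1.50 | 6.7% | 27.4% | 29.7% | 43.0% | 79.2% |
| 1.28 | 10% | 35.1% | 36.4% | 49.4% | 79.2% |
| 0.84 | 20% | 52.3% | 46.6% | 58.7% | 79.2% |

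As a share of the 79.2%, the Fisher loss is (79.2 − 23.9)/79.2 = 70% at p_C = 5%, 54% at 10% and 41% at 20%. The chi-squared loss at the same three cuts is 52%, 38% and 26%. With no placebo events, Fisher needs 5 of 20 telmisartan participants with the event (p = 0.047); 4 of 20 gives p = 0.106.

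**Step 3: adjusting for day 1.** With an assumed correlation of 0.5, the effective d is 0.9/√(1 − 0.25) = 1.039, and single-visit power is 89%.

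**Step 4: all visits.** AEs accrue through day 21, so a single-visit rate understates the graded analysis. Simulation (4,000 runs per setting; constant shift at the three later visits; equal correlation of 0.5 or 0.7 between visits, assumed) compared Fisher on any new exceedance with the day-1-adjusted mean of the later values.

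| Shift | p_C per visit | Fisher, any new event | Adjusted means |
|---|---|---|---|
| 0.9 SD | 1% | 10–15% | about 99% |
| 0.9 SD | 2.5% | 31–38% | about 99% |
| 0.9 SD | 5% | 43–48% | about 99% |
| 0.9 SD | 10% | 52–56% | about 99% |
| 0.5 SD | 1–10% | 0.4–17% | 65–79% |

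**Step 5: a smaller shift, single visit.** At 0.5 SD the noncentrality is 0.5 × √10 = 1.581 and the t-test has 33.8% power. Fisher has 14% or less over the cuts in Step 2.

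**The case against.** **The plan is not confined to grades.** A reader might infer that the two values are used solely as graded AEs. The documents do not support that. Sections 9.3.1, 9.3.6 and 9.3.10 allow for safety averages with intervals, plots by arm and listings of values. The analyte list in 6.4.2 is also open to change. What can be said is narrower: none of these provisions sets an arm comparison or a change from baseline for potassium or creatinine.

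**The loss need not be most of the power.** A reader might infer that grading discards most of it. That holds with Fisher when about 5% or fewer of placebo participants exceed the cut. This is plausible, because 5.2 excludes self-reported chronic kidney disease and potassium supplements, but it is not documented. At 10% to 20% the single-visit loss is 26% to 54%, depending on the test. The 8% is a single-visit Fisher figure; counting any new event over the visits gives more, although the continuous analysis gains too.

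**Continuous values would not necessarily reveal a real shift.** At 0.5 SD a single-visit comparison of means has about 34% power.

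**Grades and means answer different questions.** Grades capture the extreme values that matter for the individual. This stands, and is why the mean comparison belongs beside the graded table and not in its place.

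**The named risks are conditional.** Section 2.2.1 stresses hyperkalaemia in patients with advanced renal or cardiac disease, and ties renal impairment to NSAIDs. Results are also reviewed within 24 hours (7.6.1). This lowers the urgency. It does not supply an arm comparison.

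**Conclusion.** The point holds as a gap in specification. Section 9 plans no continuous between-arm analysis of potassium or creatinine, although the values will be in hand at four visits and 2.2.1 names the related risks.

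Grading gave lower power to detect a mean shift in every setting examined. The central comparison is Fisher power of about 8% to 47%, against 79% for means, at a single visit with 20 per arm and an assumed 0.9 SD shift, as the assumed placebo exceedance goes from 2.3% to 20%. The gap narrows with chi-squared. Its size rests on assumed cuts, normal values and a borrowed effect size, so it should be quoted as a range.

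This is a cheap improvement to the analysis of a pilot sized on feasibility. It is not evidence that participant monitoring is deficient.

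**What to change.** Add to 9.3.4, beside the graded tabulation: for potassium and for creatinine, the arm difference at days 4, 10 and 21 from one repeated-measures model per analyte with the day 1 value as covariate, reported as estimates with 95% CIs, labelled descriptive and without significance claims. Keep the graded tables.

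Leave 7.4.4 unchanged. It belongs to the reporting procedures and is not the place to designate an analysis.

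The cost is a few extra tables from data already collected, with no new tests or visits. The downside is that six intervals (two analytes × three visits) unadjusted for multiplicity carry some risk of a chance difference, which the descriptive label should make plain.

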9.3.5 ADHERENCE AND RETENTION ANALYSES

Participants' compliance to study medication will be monitored at each study visit via Symptom Form that is completed by the participant daily. The participant is asked to enter the date and time they take the study medication each day on the Symptom Form. The number of subjects who discontinue study

drug, withdraw completely from the study, or are lost to follow-up will be summarized in a table as counts and proportions with 95% exact confidence intervals. The specific reasons for withdrawing or lost to follow-up will also be presented.

9.3.6 BASELINE DESCRIPTIVE STATISTICS

Demographic and clinical variables will be summarized using descriptive statistics. Continuous variables will be summarized with means and standard deviations. Categorical variables will be summarized with frequencies and proportions. To understand if imbalance at the baseline, clinical and demographic variables will be compared between two-groups, appropriately, using T-tests (or Wilcoxon Rank Sum test) and chi-squared test (or Fisher's exact test). Additionally, graphical techniques will be used to visualize longitudinal profiles of study participants, stratified by treatment groups.

9.3.7 PLANNED INTERIM ANALYSES

The proposed study will be a pilot study to explore early evidence for the clinical efficacy and safety of telmisartan in mitigating the pulmonary and cardiac severity of disease due to COVID-19. Since the study will be conducted using a relatively small sample size, the research team does not intend to propose a pre-planned interim analysis for stopping for the efficacy. However, the study can be stopped at any point for the safety of participants.

9.3.8 ADDITIONAL SUB-GROUP ANALYSES

Sub-group analysis by age, sex, race/ethnicity will be performed as possible within the relatively small sample size of this study. Average treatment effect differences among subgroups (e.g. baseline severity) will be summarized, along with 95% confidence intervals. Additionally, subgroup analysis results will be visualized using graphical techniques.

9.3.9 MULTIPLE COMPARISON/MULTIPLICITY

The multiplicity error in exploratory analyses will be corrected via the false discovery rate.

9.3.10 TABULATION OF INDIVIDUAL RESPONSE DATA

Individual participant data will be listed by measure and time point.

9.4 SAMPLE SIZE

The sample size estimation for the proposed study is not provided considering that this is a pilot study. A total sample of 40 participants will be used in the study (20 per group). The above sample size was determined based on the feasibility assessment. Suppose, in the placebo group, the vector of probabilities for observing the ordinal scale outcomes is {0.40, 0.40, 0.05, 0.04, 0.04, 0.04, 0.03}, respectively for categories 1-7. If we assume the corresponding vector for the experimental treatment group as {0.76, 0.18, 0.02, 0.01, 0.01, 0.01}, that will produce an odds ratio of 5.0 between the two groups. In this scenario, we will have about 80% power to detect a treatment difference using the proportional odds model at 5% type-I error. Also, the selected sample size will allow us to detect a standardized effect size of 0.9 at Cohen's d scale, above 80% power, for a mean comparison between two groups via a two-sample T-test for a Gaussian outcome.

9.5 MEASURES TO MINIMIZE BIAS

9.5.1 ENROLLMENT/ RANDOMIZATION/ MASKING PROCEDURES

After signing the Informed Consent Form (ICF), the subject is assigned a unique patient identifier number (PID). At the time of enrollment (randomization), the subject is assigned a unique subject identifier number (SID). PIDs and SIDs are not re-assigned. Screening Numbers and Subject Numbers are not re-assigned. Subjects are randomly allocated (1:1) to active medication (telmisartan) or placebo.

Randomization may occur after verbal informed consent has been obtained from the subject or representative, and subject eligibility has been confirmed. A study enrollment form will be sent to the research pharmacist to initiate the randomization process and assign the treatment to the participant. The research pharmacist will obtain the randomized treatment allocation from a computer-generated randomized treatment list for the subject and the pharmacist or designated staff will prepare the study medication. The study medication will not be provided to the participant however until a written informed consent is obtained. The site research staff and investigators (with the exception of the research pharmacist) will not have access to the treatment assignments and investigational drug products are over-encapsulated to blind the study drugs.

Since the research pharmacist is unblinded in order to provide the assigned treatment, the research pharmacist will not be involved with the assessment of outcomes or data capture except as necessary to manage drug distribution, control and accountability.

9.5.2 EVALUATION OF SUCCESS OF BLINDING

Not applicable.

9.5.3 BREAKING THE STUDY BLIND/PARTICIPANT CODE

Blinded Treatment assignments will be made available to the Investigators only in the event of a medical emergency where knowledge of the blinded treatment is necessary for further medical management of the participant (for instance in the event of serious adverse event). The rationale for unblinding and circumstances supporting unblinding must be documented in the research record. A written request to unblind will be sent by the investigator to the research pharmacist or designated pharmacy staff. The treatment assignment will be revealed to the investigator in writing and documentation will be filed in the accountability record.

10 SOURCE DOCUMENTS AND ACCESS TO SOURCE DATA/DOCUMENTS

Source data is defined as information, original records of clinical findings, observations, or other activities in a study necessary for the reconstruction and evaluation of the study. CRF will be designed by the research nurse coordinator and will serve as source documents for some of the required data except for the source data from participant's medical records, hematology, chemistry, and EKG results.

The research nurse coordinator and research pharmacist will maintain the source data, CRF, and all regulatory documents in compliance with ICH E6 and regulatory and institutional requirements for the protection of confidentiality of participants. The participant's research records will be stored in a locked file cabinet in the research unit's main office. PI, Co-I, research nurse coordinator, research pharmacist, and research staff working on the protocol or data analyses will have access to all documents and will adhere to all requirements for subject confidentiality as outlined in the ICF. **QUALITY ASSURANCE AND QUALITY CONTROL**

This section indicates the plans for quality management, the system for assessing the quality of processes within the study. Quality management will encompass quality assurance (QA) and quality control (QC). QA is defined as all planned and systematic actions that are established to ensure that the trial is performed and the data are generated, documented (recorded), and reported in compliance with Good Clinical Practice (GCP) and the applicable regulatory requirement(s) (ICH E6 1.46). QC is defined as the operational techniques and activities undertaken within the quality assurance system to verify that the requirements for quality of the trial-related activities have been fulfilled (ICH E6 1.47).

The research unit has a written QA and QC management plan that will be used for this protocol.

QC procedures will be implemented beginning with the data entry system and data QC checks that will be run on the database will be generated. Any missing data or data anomalies will be clarified/resolved by the PI in collaboration with the research nurse coordinator and research pharmacist.

The PI, research nurse coordinator, and research pharmacist will verify that the clinical trial is conducted and data are generated, documented (recorded), and reported in compliance with the protocol, GCP, and the applicable regulatory requirements (e.g., Good Laboratory Practices, GLP).

The investigational site will provide direct access to all trial related sites, source data/documents, and reports for the purpose of monitoring and auditing by local and regulatory authorities.

11 ETHICS/PROTECTION OF HUMAN SUBJECTS

11.1 ETHICAL STANDARD

The PI will ensure that this study is conducted in full conformity with Regulations for the Protection of Human Subjects codified in 45 CFR Part 46, 21 CFR Part 50, 21 CFR Part 56, and the ICH E6.

11.2 INSTITUTIONAL REVIEW BOARD

The protocol, informed consent form(s), recruitment materials, and all participant materials will be submitted to the IRB for review and approval. Approval of both the protocol and the consent form by the IRB must be obtained before any participant is enrolled.

Any amendment to the protocol will require review and approval by the IRB before the changes are implemented to the study. All changes to the consent form will be IRB approved; a determination will be made regarding whether previously consented participants need to be re-consented.

11.3 INFORMED CONSENT PROCESS

11.3.1 CONSENT/ASSENT AND OTHER INFORMATIONAL DOCUMENTS PROVIDED TO PARTICIPANTS

IRB-approved informed consent document describing in detail the study intervention, study procedures, and risks will be given to the participant and written documentation of informed consent will be required prior to starting intervention/administering study intervention.

The informed consent document for this study is submitted with this protocol.

11.3.2 CONSENT PROCEDURES AND DOCUMENTATION

For each study subject, an oral consent will be obtained prior to obtaining any patient information needed to determine eligibility requirements and for any specific protocol related information. A signed written informed consent will be obtained at the Entry visit. The process will be fully documented in the source documents.

The research nurse coordinator, PI or Co-I will explain orally the nature, duration, and purpose of the study, and the action of the drug in such a manner that the subject is aware of the potential benefits, risks, inconveniences, and adverse effects that may occur because of their participation. They will be informed that the subject may withdraw from the study at any time. They will receive all information that is required by federal, state, and local laws and regulations and ICH guidelines.

The participant will also be asked to read and review the IRB-approved informed consent document and to ask questions prior to signing. An opportunity will be given for the participant to discuss the study with their significant other and/or primary care physician or think about it prior to agreeing to participate. The participant will sign the informed consent document prior to invasive procedures specifically for the study. The participant may withdraw consent at any time throughout the course of the trial.

The participant will retain the signed informed consent document and a photo will be taken of the signed consent for the research record. The rights and welfare of the participants will be protected by emphasizing to them that the quality of their medical care will not be adversely affected if they decline to participate in this study.

11.4 PARTICIPANT AND DATA CONFIDENTIALITY

Participant confidentiality is strictly held in trust by the participating investigators and research staff. This confidentiality is extended to cover testing of biological samples in addition to the clinical information relating to participants. Therefore, the study protocol, documentation, data, and all other information generated will be held in strict confidence. No information concerning the study or the data will be released to any unauthorized third party without the permission of the Principal Investigator.

All subjects will be assigned a unique patient identifier number (PID) and at the time of enrollment (randomization), each subject will be assigned a unique subject identifier number (SID). PID and SIDs are not re-assigned. The log that links the subject's name to the PID is stored in a locked file cabinet. This information is also stored on a separate flash drive and not on a computer hard drive or server. The locked file cabinets housing these confidential documents will be stored in research unit's main office, which is in a 24-hour secured building. The only individuals who have access to these locked files are authorized personnel of the research staff directly involved in this study.

Representatives of the IRB or FDA may inspect all documents and records required to be maintained by the PI, including but not limited to, medical records (office, clinic, or hospital) and pharmacy records for the participants in this study.

If the study participant elects to have their clinical laboratory data sent to their primary care providers, they will be asked to sign a separate consent covering release of his/her data to their physician.

The study participant's contact information will be securely stored in a locked file cabinet for internal use during the study. At the end of the study, all records will continue to be kept in a locked file cabinet in the main office of the research unit for as long a period as dictated by local IRB and Institutional regulations.

A study database containing de-identified study participant research data only will be utilized for the purposes of statistical analysis and scientific reporting. The database will not include the participant's contact or identifying information. Rather, individual participants and their research data will be identified by a unique study identification number. The study data entry and study management systems used by research staff will be secured and password protected.

